13 DATA MANAGEMENT

13.1 Data Collection and Management

Data will be entered into the eCRF. Clinical data will be managed in accordance with the data management plan to ensure that the integrity of the data is maintained. Adverse events and medical history will be coded using the Medical Dictionary for Regulatory Activities (MedDRA). Concomitant medications will be coded using the WHO Drug Dictionary (WHO-DD).

13.1.1 Historical and Concurrent Control Data

The historical and concurrent control data used for exploratory OD comparison analyses will be provided by Virginia Commonwealth University as an anonymized data extract from their electronic medical record system beginning in 2015. Data will include, but not be limited to; demographics, discharge diagnoses and status and ICD 9/10 codes.

13.1.2 Database Quality Assurance

The eCRFs will be reviewed and checked for omissions, apparent errors, and values requiring further clarification using computerized and manual procedures. Data queries requiring clarification will be generated and addressed by the investigational site. Only authorized personnel will make corrections to the eCRFs, and all corrections will be documented.

13.1.3 Source Documents

The Investigator is responsible for the quality of the data recorded in the CRFs. The data recorded should be a complete and accurate account of the subject's record collected during the study.

Study data are to be gathered onto primary source documents at the clinical site, except for certain assessments to be captured as direct entry on a tablet as indicated in the next paragraph. Completion of source documents will precede the completion of the CRF. Source documents may be electronic, hard copy, or a combination of both and are defined as the results of original observations and activities of a clinical investigation. Source documents will include, but are not limited to, progress notes, electronic data, screening logs, and recorded data from automated instruments. All source documents pertaining to this study will be maintained by the Investigator and made available for direct inspection by the authorized study personnel outlined in the ICF. The CRF will be considered the source document for individual CRF elements such as study-specific scales if those data are collected directly onto a CRF.

The following assessments will be collected as direct data entry:

- HCRUQ
- COWS
- OC-VAS

- Opioid Demand Task
- Delay Discounting Task
- HEOR assessments

14 STATISTICS

14.1 General Procedures

This section describes methods for sample size determination, analysis populations and planned analyses. Additional unplanned analyses may be required after all planned analyses have been completed. Any unplanned analyses will be clearly identified in the clinical study report.

Continuous variables will be summarized using descriptive statistics such as means, standard deviations (SD), medians, minimums, and maximums. Categorical variables will be reported as frequency counts (including number missing) and the percentage of subjects in the corresponding categories. Individual subject data will be presented by subject in data listings. Data listings will include all data collected from the initial screening visit to the end of the study for all subjects enrolled.

14.2 Sample Size

The study will be powered based upon the primary endpoint, repeat opioid OD and death compared to historical and concurrent control data.

Rationale for sample size: Power calculations: sample size was calculated based on a primary outcome measure of reduced repeat opioid OD rates. Previous research has shown self-reported repeat lifetime OD rates of 15-23% for patients who were seen for an opioid OD (Morizio, Baum et al. 2017).

Based on VCU health system data, for patients seen in the ED for an opioid OD in 2016, 11.5% of those patients were either seen again in the ED for an opioid OD or had died based on Virginia Department of Health death registry data within 6 months after their initial ED visit. Based on power calculations below, with a 3% repeat OD or death rate for the novel treatment group vs. the 11.5% treatment as usual rate in the historical control group, with 99 participants in the novel treatment group and 198 participants in the historical control group there will be a power of 80% at a type I error rate of 5%. See table below. If there is a less than 3% repeat OD rate in the intervention group there will be greater than 80% power.

Fixed Power of 0.80 and sample size for equivalent or non-equivalent numbers of participants per group (intervention vs. historical treatment as usual)

repeated OD/death rate	Stat method	n1:n2 (1:1, 2:1 or :1 ratio)		
11.5% vs 2%	Z-test	86:86	117:59	148:49
	Nonparametric	94:94	148:74	198:66
11.5% vs 3%	Z-test	115:115	160:80	204:68
	Nonparametric	131:131	198:99	265:88

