6 STUDY CONDUCT

6.1 Subject Enrolment

Study participation begins once written informed consent is obtained; a subject ID is then assigned. The subject ID will be used to identify the subject during the screening process and throughout study participation, if applicable.

The Investigator is responsible for maintaining a master list (i.e., a subject identification list) of all consented subjects and will document all subjects that did not meet study eligibility criteria (i.e., screen failures), including reason(s) for ineligibility (i.e., a subject screening and enrolment log). Ineligible subjects, as defined by the protocol-specific inclusion and exclusion criteria, should not receive SUBLOCADE and should be documented as screen failures.

Controls will be selected from OD ED VCU visits beginning in 2015. The dataset will be anonymized; therefore, consent is not required and will not be obtained.

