14.7 Efficacy Analysis

14.7.1 Primary Efficacy Analysis

The repeat opioid OD or opioid-related death primary endpoint analysis will be performed using Cox proportional regression and compare the SUBLOCADE treatment arm to historical and concurrent control data. Propensity scores will be used to match study participants to controls. Repeat OD and deaths (measured as time-to-event or censored at 6 months post index OD) will be tracked using subject reports, electronic medical records and state death registries. Events will be counted within the 6 months of treatment period for all treated subjects.

Propensity score analysis will be used in the analysis of SUBLOCADE vs. the control for time to repeat OD or opioid-related death. Study subjects will receive a propensity score that will be matched to propensity scores in the control data. The propensity score, p , will also be used as a weight in the Cox proportional hazards model. All SUBLOCADE treatment group subjects will have a weight of $p=1$ and patients in the control groups will be weighted by $p/(1-p)$. Here p can be viewed as the probability that the control subject would have been a study participant if the study were performed during their treatment.

The propensity score will be estimated by fitting a logistic regression on a dataset consisting of the consenting subjects (subjects in the SUBLOCADE arm at VCU) and the controls. The response variable will be consent to treatment; predictors will include baseline characteristics such as subject age, gender, county, race and insurance status. This model will be used to generate the predicted probability of consent to participate among the controls.

The Cox proportional hazards model will use the controls as the reference group and code the SUBLOCADE arm as a factor variable. The analysis will test the coefficient for the SUBLOCADE arm versus the controls from the Cox regression, with the interpretation of the exponential (coefficient) as the hazard ratio for time to repeat OD or opioid-related death in subjects consenting to the active treatment group versus the control cohorts.

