The probabilities for the control cohort will be used as weights in the Cox proportional hazards model. The weights serve to make the control cohort appear similar to the treatment group on the observed baseline characteristics; this will be checked using covariate balance diagnostics. The weights will provide greater weight for control patients who likely would have participated if offered a prospective trial of SUBLOCADE and lesser weight for patients unlikely to have consented.

In addition, the results will be illustrated with a Kaplan-Meier curve.

The analysis will take place once all subjects have completed the trial and sufficient time has passed to allow the state death registries to be updated.

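### The 80% power in 14.2 is for an unweighted comparison of 99 with 198 patients. It is not supported for the p/(1-p)-weighted Cox test planned in 14.7.1 if only 198 controls are used

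*Combined protocol and SAP*

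**What the plan says.** **Power (14.2).** The control rate comes from 2016 data from the trial's own health system, where "11.5% of those patients were either seen again in the ED for an opioid OD or had died" within six months. The design case is "with a 3% repeat OD or death rate for the novel treatment group vs. the 11.5% treatment as usual rate in the historical control group", for which "with 99 participants in the novel treatment group and 198 participants in the historical control group there will be a power of 80" per cent. The type I error rate is 5%, with sidedness not stated. The 198:99 figure is the entry in the table row labelled only as nonparametric.

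**Analysis (14.7.1).** The primary analysis "will be performed using Cox proportional regression and compare the SUBLOCADE treatment arm to historical and concurrent control data". Treated subjects have weight 1, and "patients in the control groups will be weighted by" p/(1-p). Unequal weighting is the purpose: "The weights will provide greater weight for control patients who likely would have participated if offered a prospective trial of SUBLOCADE", and less weight for those unlikely to have consented. The same section also says that propensity scores will be used for matching. Balance diagnostics are planned.

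**Control pool (6.1).** "Controls will be selected from OD ED VCU visits beginning in 2015". Concurrent patients who decline treatment are also controls. No total is given, and 14.7.1 sets no limit of 198.

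**Not stated anywhere:** the expected spread of the weights, an effective control size, whether the coefficient is tested by Wald or score, the variance estimator, and how matching and weighting combine.

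**The concern.** The power calculation and the primary analysis are different procedures. The first gives each of the 198 controls a full weight of one. The second gives controls unequal weights, and n unequally weighted observations carry less information than n equally weighted ones. The less the treated subjects resemble the controls, the more the weighting is needed and the more it costs.

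Some separation is plausible. Treated subjects pass a long list of exclusions and may enter by ambulance referral without an ED visit, whereas controls are ED visits from 2015 onward.

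The consequence is mainly for interpretation. A null primary result would be read against a power figure computed for a test that was not run. The number of controls is also the one quantity that could be raised cheaply, because controls are anonymised records that need no consent.

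**Working it through.** **Inputs from 14.2:** control risk 11.5%, treated risk 3%, 99 treated, 198 controls, alpha 5%. **From 14.7.1:** Cox model, weights 1 and p/(1-p), censoring at six months. **Assumed, because the documents are silent:** propensity c-statistic 0.60 to 0.75, exactly 198 controls in the model, exponential event times, covariates unrelated to outcome, robust variance, no matching step.

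**1. Reproduce the plan's figure.** Fisher's exact test was enumerated over two binomials, 198 at 0.115 and 99 at 0.03. At one-sided 5% the power is 80.25%. All six entries in the nonparametric rows reproduce this way at 80.1–80.3%, so the table contains no arithmetic slip. A two-sided 5% Fisher test gives 73.0% for the same design, so the 80% already depends on a one-sided test that the plan does not state. The steps below hold alpha at one-sided 5%, to isolate the effect of weighting.

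**2. Effective number of controls.** ESS = (Σw)² / Σw². Let the propensity linear predictor be normal in controls with SD s, and shifted by s² in treated subjects. Then s = √2·Φ⁻¹(c), and for large samples ESS ≈ n·exp(−s²):

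- c = 0.60: s² = 0.128, so 198 × 0.880 = 174
- c = 0.65: s² = 0.297, so 198 × 0.743 = 147
- c = 0.70: s² = 0.550, so 198 × 0.577 = 114
- c = 0.75: s² = 0.910, so 198 × 0.403 = 80

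Fitting a five-covariate logistic model in each simulated trial adds noise to the weights. The simulated means are 162, 137, 108–109 and 80. With no true separation at all (c = 0.50), the mean is 183.

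**3. Rough check.** Putting the reduced control size into the plan's own Fisher test gives 74.9% at 137 controls and 62.3% at 80.

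**4. Simulate the planned model.** The hazard ratio implied by the design is ln(0.97)/ln(0.885) = 0.25. The propensity score is refitted in each replicate, controls are weighted p/(1-p), and the Cox coefficient is tested with a robust variance. Ranges cover repeated runs of about 3,000 replicates; Monte Carlo standard error is about 0.8 points.

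| 198 controls, one-sided 5% | Effective controls | Robust Wald | Robust score |
|---|---|---|---|
| Unweighted | 198 | 79% | 89–90% |
| c = 0.60 | 162 | 76–79% | 87–89% |
| c = 0.65 | 137 | 74–76% | 85% |
| c = 0.70 | 108–109 | 71–73% | 81–82% |
| c = 0.75 | 80 | 67–69% | 74–76% |

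The two tests differ because events are few. The expected number of treated events is 99 × 0.03 = 2.97, and the chance of none is 0.97⁹⁹ = 4.9%. The Wald column does not count zero-event samples as rejections. Counting them gives 81%, 79%, 78% and 74% down the column, against 84% unweighted.

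**5. Larger control pools.** With 266, 343 and 492 controls at c = 0.65, 0.70 and 0.75, the effective size returns to about 185–196. One-sided power is then about 79–80% (Wald) or 90–91% (score). With 600 controls, Wald power is about 85–86% at c = 0.65 and 81–82% at c = 0.75.

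**The case against.** A reader might infer that the weights shrink the 198 controls to some 80–137 effective patients and that the trial therefore misses its 80%. The documents do not support that, for four reasons.

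- **The range is assumed.** Nothing in the plan gives the discrimination of a model built on age, gender, county, race and insurance. At c = 0.60 the effective size is still about 162, and Wald power is at most about 3 points below its unweighted value.
- **The plan does not cap the analysis at 198.** That number appears only in 14.2. Records from 2015 onward plus concurrent decliners could exceed it, and a moderately larger pool removes the loss.
- **The test is not named.** A robust score test stays above 80% up to about c = 0.70 with only 198 controls. The robust Wald test is already at 79% unweighted, so part of its gap from 80% comes from the choice of test and not from the weights.
- **Matching is left out of the simulation.** With 2:1 nearest-neighbour matching of 198 controls from assumed pools of 400–1,000, at c = 0.65–0.75, the effective size is about 174–195 if the propensity model is refitted in the matched set. It is about 103–150 if the original scores are kept. The plan does not say which applies.

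All four points stand, and they limit the conclusion. They do not remove the mismatch: 198 is the only control number tied to the power claim, and no section allows for weighting.

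**Conclusion.** The point holds as a mismatch between the power method and the analysis method, with a loss of conditional size. The 80% belongs to an unweighted, one-sided 5% comparison of proportions. For the weighted Cox test with 198 controls it is unsupported, which is weaker than saying it is missed in every case.

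Across the assumed c-statistic range, weighting costs up to about 10–12 points with a Wald test and up to about 13–16 with a score test. Whether power ends below 80% depends on the test, the control pool and the handling of matching, all of which the plan leaves open. Sidedness is a separate gap. With a two-sided 5% test and 198 controls, the weighted figures at c = 0.65 and 0.75 are 61.9% and 52.3% (Wald), or 77.8% and 60.3% (score).

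The figures assume that covariates are unrelated to outcome and would change if they predict it.

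**What to change.** 1. In 14.2 and 14.7.1, state that all eligible controls in the health-system extract enter the analysis with p/(1-p) weights, in place of a 198-record control group. Reconcile this with the sentence on propensity matching: either drop matching, or say how it combines with weighting and whether the score is refitted. Report the effective control size alongside the balance diagnostics.
2. In 14.2, replace the 80% with the power of the weighted Cox test that will be run. Name Wald or score, the variance estimator and the sidedness, and show power over a range of effective control sizes. No single replacement figure should be written in now, because any such figure would build in an assumed c-statistic and a test that the plan has not chosen.

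The cost is wording in two sections and a short simulation. No patients, visits or consents are added, since the extra records come from the anonymised extract already planned. There are two downsides: the stated power may be less favourable, and the gain depends on the number of eligible controls, which the documents do not give.

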14.3 Statistical Hypotheses

14.3.1 Primary Endpoint

The primary hypothesis is that SUBLOCADE is superior to the historical and concurrent control group for rates of repeat OD and death during the 6 months treatment period.

14.4 Analysis Populations

14.4.1 Treatment Population

The Treatment Population includes all subjects who receive at least 1 dose of study medication. This population will be used for all safety and efficacy analyses. In the safety analyses, subjects will be analysed according to treatment actually received.

14.5 Planned Analyses

The analysis will take place once all subjects have completed the trial and sufficient time has passed to allow the state death registries to be updated.

14.6 Demographic and Baseline Characteristics Analyses

Demographic and baseline characteristics, including gender, race, age, weight, height and disease history will be summarized by treatment group using descriptive statistics. Disease history will include but is not limited to drug use history, history of MAT and previous Ods. Qualitative variables, e.g. gender and race will be summarized using frequencies; quantitative variables, e.g. age, weight, height will be summarized using e.g. mean, SD, median, minimum and maximum.

14.7 Efficacy Analysis

14.7.1 Primary Efficacy Analysis

The repeat opioid OD or opioid-related death primary endpoint analysis will be performed using Cox proportional regression and compare the SUBLOCADE treatment arm to historical and concurrent control data. Propensity scores will be used to match study participants to controls. Repeat OD and deaths (measured as time-to-event or censored at 6 months post index OD) will be tracked using subject reports, electronic medical records and state death registries. Events will be counted within the 6 months of treatment period for all treated subjects.

Propensity score analysis will be used in the analysis of SUBLOCADE vs. the control for time to repeat OD or opioid-related death. Study subjects will receive a propensity score that will be matched to propensity scores in the control data. The propensity score, p , will also be used as a weight in the Cox proportional hazards model. All SUBLOCADE treatment group subjects will have a weight of $p=1$ and patients in the control groups will be weighted by $p/(1-p)$. Here p can be viewed as the probability that the control subject would have been a study participant if the study were performed during their treatment.

The propensity score will be estimated by fitting a logistic regression on a dataset consisting of the consenting subjects (subjects in the SUBLOCADE arm at VCU) and the controls. The response variable will be consent to treatment; predictors will include baseline characteristics such as subject age, gender, county, race and insurance status. This model will be used to generate the predicted probability of consent to participate among the controls.

The Cox proportional hazards model will use the controls as the reference group and code the SUBLOCADE arm as a factor variable. The analysis will test the coefficient for the SUBLOCADE arm versus the controls from the Cox regression, with the interpretation of the exponential (coefficient) as the hazard ratio for time to repeat OD or opioid-related death in subjects consenting to the active treatment group versus the control cohorts.

The probabilities for the control cohort will be used as weights in the Cox proportional hazards model. The weights serve to make the control cohort appear similar to the treatment group on the observed baseline characteristics; this will be checked using covariate balance diagnostics. The weights will provide greater weight for control patients who likely would have participated if offered a prospective trial of SUBLOCADE and lesser weight for patients unlikely to have consented.

In addition, the results will be illustrated with a Kaplan-Meier curve.

The analysis will take place once all subjects have completed the trial and sufficient time has passed to allow the state death registries to be updated.

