- 3) Patients who are seen only by EMS personnel and are given an opioid antagonist for opioid OD but refuse transport to an Emergency Department but would like to be considered for the VOTIVE study will be given a referral card by EMS personnel. Patients who present to the ED or who are admitted to the inpatient unit for an Opioid OD and would like to be considered for the VOTIVE study but who are not approached by the study team (i.e. outside of business hours) will be given a referral card by a healthcare provider. The patient may present to the clinic within 7 days (168 h) of OD event for evaluation and initial screening visit.

In the clinic, subjects will be consented if they express interest in participating in the study. If participants meet study inclusion criteria and none of the exclusion criteria they will be administered 4 mg/1 mg SUBOXONE sublingual film followed by a 1-hour wait. If the subject displays no allergic/hypersensitivity reaction to SUBOXONE sublingual film after 1 hour, SUBLOCADE (300 mg) will be administered in the clinic. Subjects will remain in the clinic for 1 hour after the SUBLOCADE injection and are clinically stable (respiratory rate [RR] ≥ 12 , pulse oximetry $> 95\%$, Glasgow Coma Scale [GCS] score of 15. A COWS assessment and AEs will be collected prior to SUBLOCADE administration and 1-hour post SUBLOCADE prior to discharge. Participants with initial COWS < 8 and who were released from a controlled environment within the past 30 days, will remain in the outpatient clinic for 2 hours after 300 mg SUBLOCADE to assess for sedation using the Richmond Agitation-Sedation Scale. Patients will be discharged if RASS is 0 or greater. Patients who present with abnormal vital signs, or sign of sedation will remain in clinic or will be transferred to the ED until they are safe for discharge from the medical facility. If participants experience precipitated withdrawal, they will be treated symptomatically with medication as described in section 8.4 below.

Upon discharge, patients will be instructed to use over the counter ibuprofen and acetaminophen as needed. They will also be provided with two oral doses of 50 mg of hydroxyzine as ancillary medications if needed in the judgement of the clinician.

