[figure not shown]
The primary analysis will be performed on the primary and key secondary endpoints after all subjects have been enrolled and completed the end of treatment visit. An enrolled subject is defined as a subject who has received at least one dose of SUBLOCADE.

STUDY SCHEMATIC

[figure not shown]
Figure 1 Study Schematic for SUBLOCADE Initiated in Emergency Department

- Participants who decline to be enrolled in the study will receive care as determined by the ED physicians and continue to be passively followed for 24 weeks. Passive follow-up will include tracking for treatment initiation and engagement and repeat OD via anonymized medical records and tracking for death using state death registries.
- Injection 2 will be 300 mg and will occur on Day 8 (-0 /+4 days); Injections 3-7 will remain 300 mg (or 100 mg if unable to tolerate 300 mg as determined by study investigator) administered at 28-day (-2/+4 days) intervals.
- Intervention subjects will receive a safety follow-up telephone call 30 days after their EOT/ET visit to assess AEs, SAEs, pregnancy status (if applicable) and concomitant medications. Subjects who decline to continue in MAT will receive monthly safety follow-up phone calls for an additional 5 months (6 months total) to assess SAEs, pregnancy status (if applicable) and concomitant medications.

Figure 2 Study Schematic for SUBLOCADE Initiated in Inpatient Unit

- Participants who decline to be enrolled in the study will receive follow-up care as determined by the inpatient unit physicians and continue to be passively followed for 24 weeks. Passive follow-up will include tracking for treatment initiation and engagement and repeat OD via anonymized medical records and tracking for death using state death registries.
- Injection 2 will be 300 mg and will occur on Day 8 (-0/+ 4); Injections 3-7 will remain 300 mg (or 100 mg if unable to tolerate 300 mg as determined by study investigator) administered at 28-day (-2/+ 4 days) intervals.
- Intervention subjects will receive a safety follow-up telephone call 30 days after their EOT/ET visit to assess AEs, SAEs, pregnancy status (if applicable) and concomitant medications. Subjects who decline to continue in MAT will receive monthly safety follow-up phone calls for an additional 5 months (6 months total) to assess SAEs, pregnancy status (if applicable) and concomitant medications.

Figure 3 Study Schematic for Initial Dose of SUBLOCADE in Clinic

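### Section 14.7.1 gives two unreconciled six-month windows and no delayed entry at first injection, which tilts the comparison with historical controls slightly towards SUBLOCADE

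*Combined protocol and SAP*

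**What the plan says.** The primary endpoint in section 3.1 is a time to repeat overdose or opioid-related death, with no starting point given there. Section 14.7.1 supplies two windows in consecutive sentences:

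- Follow-up is "measured as time-to-event or censored at 6 months post index OD".
- "Events will be counted within the 6 months of treatment period for all treated subjects".

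Other sections lean one way or the other. The primary hypothesis (14.3.1) is superiority "for rates of repeat OD and death during the 6 months treatment period". The 11.5% control rate in 14.2 counts events "within 6 months after their initial ED visit". Table 2 sets the analysis at EOT and labels that 6 months, while section 4.2 puts EOT at 7 months and Appendix 2 puts it at Day 169. The schematic notes follow decliners passively for 24 weeks.

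On who is in each arm:

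- Section 14.4.1: "The Treatment Population includes all subjects who receive at least 1 dose of study medication".
- Synopsis, Planned Analyses: "An enrolled subject is defined as a subject who has received at least one dose of SUBLOCADE".
- Section 6.2 makes a consented person who is not injected a screen failure, who may be re-screened after a later overdose.
- Synopsis, Study Design, on referred patients: "The patient may present to the clinic within 7 days (168 h) of OD event for evaluation and initial screening visit".
- Section 6.1: "Controls will be selected from OD ED VCU visits beginning in 2015".

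No section mentions delayed entry, a landmark or time-varying exposure.

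**The concern.** There are two linked problems.

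First, the two sentences can start and stop the clock on different days. A non-fatal repeat overdose between the index overdose and a later injection counts under the first sentence but not under the second. Two analysts following 14.7.1 could report different primary hazard ratios.

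Second, a treated subject must be alive at injection to be analysed at all. If that subject's time at risk starts at the index overdose, the days before injection are guaranteed survival time. They are also guaranteed event-free time wherever early non-fatal overdoses drop out: under the treatment-period rule, when the person is never dosed, or when a screen failure is re-indexed to a later overdose. A historical control who dies or overdoses in those same days counts as an event. The propensity score cannot correct this. Its named predictors (age, gender, county, race, insurance) balance baseline mix, whereas this is a feature of follow-up time.

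The Synopsis reports that repeat events cluster early, so the first days are the ones where unequal treatment matters most.

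**Working it through.** **Plan's own figure.** The pair 198:99 in section 14.2 reproduces as Fisher's exact test, one-sided 5%, 11.5% against 3%: power 80.25%. That calculation has no time origin, so nothing below depends on it. The planned rates imply a hazard ratio of ln(0.97)/ln(0.885) = 0.249.

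**Inputs from the documents.** Control six-month risk 11.5% (14.2), so the cumulative hazard is H = −ln(0.885) = 0.1222. Groups of 99 and 198 (14.2). Latest clinic presentation 168 h after the overdose (Synopsis).

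**Assumptions.**
- Six months is 182 days.
- A share f of six-month events falls by day 60. The Synopsis puts 70% of repeat events within six months and the majority in the first two months. If the majority refers to six-month events, f is just over half (0.51). If it refers to all repeat events, f is about 0.50/0.70 = 0.71.
- The hazard is flat within days 0–60 and within days 60–182.
- The earliest injection is 8 h after the overdose, taken from the 8-hour rule in section 5.4.
- The mix of injection times is not documented, so several are shown.

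**Hazards.** h1 = −ln(1 − 0.115f)/60 and h2 = (0.1222 − 60·h1)/122.
- f = 0.51: h1 = 0.001007, h2 = 0.000506 per day.
- f = 0.71: h1 = 0.001420, h2 = 0.000303 per day.

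**Control events in days 0–7.** 1 − exp(−7·h1) = 0.0070 to 0.0099, which is 6.1% to 8.6% of six-month events. In 198 controls that is 1.4 to 2.0 of 198 × 0.115 = 22.8 expected.

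**Expected Cox estimate.** Solve for β in ∫[e1 − (e0 + e1)·n1·exp(β)/(n1·exp(β) + n0)]dt = 0. Here n1 and n0 are the expected numbers at risk, and e1 and e0 the expected event rates, in treated and historical controls. Ranges run over f = 0.51 to 0.71, with all pre-injection events lost:

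| Injection times | True HR 1, clock from index OD | True HR 1, treated clock restarted at injection | Planned HR 0.249, clock from index OD |
|---|---|---|---|
| Half at 8 h, half uniform 8–168 h | 0.975–0.983 | 0.982–0.992 | 0.243–0.245 |
| Uniform 8–168 h | 0.955–0.968 | 0.967–0.985 | 0.239–0.242 |
| Everyone on day 7 (bound) | 0.914–0.939 | 0.937–0.971 | 0.229–0.235 |

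With everyone injected at 8 h, the index clock reads 0.996–0.997. Entering treated subjects at injection returns 1.000 and 0.249 in every row.

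**Hand check of the bound.** (H − 7·h1)/H = (0.1222 − 0.0071)/0.1222 = 0.942 and (0.1222 − 0.0099)/0.1222 = 0.919, close to the Cox values.

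**Sensitivity.**
- Only a quarter of pre-injection events lost, index clock: 0.994–0.996 (half/half) and 0.989–0.992 (uniform).
- Flat risk over six months, all lost: 0.988 and 0.979 on the index clock, and exactly 1.000 if the treated clock restarts at injection.

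**Test size.** With 99 against 198 and no drug effect, the simulated one-sided rejection rate in favour of SUBLOCADE is 2.3–2.6% for the half/half and uniform mixes, against a nominal 2.5%. It is 2.7–3.7% if everyone were injected on day 7 (20,000 runs, Monte Carlo error about 0.1 point).

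**Decliners.** Suppose refusal times follow the injection-time distribution and pre-refusal events are lost. The index clock then reads 1.000 against decliners. Entering treated subjects late while starting decliners at the index encounter reads 1.011–1.018, a small bias the other way.

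**The case against.** **The windows may be nearer than they look.** The first sentence of the pair points to the index overdose, and the control rate in 14.2 runs from the ED visit. The second can be read as a counting rule: include events in everyone treated, even after stopping. That reading removes part of the conflict, but it does not align where the two windows start and end. The need to state one window stands.

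**The effect is small against sampling error.** Under the planned rates about 22.8 + 99 × 0.03 = 25.8 events are expected, and the standard error of the log hazard ratio is roughly √(1/22.8 + 1/2.97) = 0.62. Moving from 0.249 to 0.239 is ln(0.239/0.249) = −0.04. The 0.96 end of the null range also needs injections spread evenly over the week and every pre-injection event lost. This stands, and it limits the severity.

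**Deaths before injection.** A reader might infer that the two windows, or the lack of delayed entry, are why such deaths never count against SUBLOCADE. The documents do not support that. Those deaths drop out because the analysis requires a dose (Synopsis, 6.2, 14.4.1), and delayed entry would not bring them back. It only stops the early days being compared unequally.

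**Decliners.** A reader might also carry the bias over to the concurrent controls. ED and inpatient candidates are approached once stable and alert, and the clinic-start schematic lists decliners too. They have their own guaranteed survival time, so this part of the concern falls largely on the historical comparison.

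**Conclusion.** The point holds, at minor to should-fix severity. Section 14.7.1 leaves the primary window open to two readings. Without delayed entry, the comparison with historical controls credits SUBLOCADE with guaranteed survival time, and with event-free time where early non-fatal overdoses are also lost.

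On the index-overdose clock this favours SUBLOCADE even if risk is flat. If the treated clock restarts at injection, it does so only if risk is front-loaded. The sizes rest on assumed event timing, injection times and the share of early events lost, none of which the documents fix.

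It would be wrong to conclude that this could create the planned 11.5% against 3% contrast, or that it invalidates the test: the false-positive rate stays near nominal for the plausible injection mixes. Nor do the documents support saying that every non-fatal overdose before injection is lost. On a plain index-overdose reading, one in a person later dosed still counts. Nothing is claimed about the net direction of all biases. Subject reports, which feed the treated arm and may be missing from an anonymized control extract, could push the other way.

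**What to change.** In section 14.7.1, with 14.3.1 and Table 2 aligned to it:

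1. State one time origin, the index overdose, and one censoring day for all arms, no later than the 24 weeks (168 days) for which decliners are followed. Delete the treated-only window.
2. In the Cox model and the Kaplan-Meier curve, enter SUBLOCADE subjects into the risk set at first injection and historical controls at the index encounter.
3. Enter decliners at their approach or refusal time. If that is not recorded, either use a common landmark such as day 7 in both arms for the decliner comparison, or draw decliner entry times from the treated overdose-to-injection distribution and require decliners to be event-free at the drawn time.
4. State one rule for a non-fatal repeat overdose before entry and apply it to all arms, including re-screened subjects.

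**Cost.** SAP wording and an entry-time variable. Overdose and injection times for treated subjects are already needed to verify the 168 h limit. The control extract must carry index and event dates and times. Section 13.1.1 does not name them, but its list is open-ended. Approach or refusal times for decliners may need to be recorded. About 1.4 to 2.0 of the 22.8 expected control events may leave the comparison, and the effect may look slightly smaller. A day-7 landmark, where used, also drops on-treatment events before day 7.
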